### 15. STUDY ADMINISTRATION

## 15.1 STUDY INVESTIGATORS

Participating Investigators will be qualified based on professionals experienced in treatment of gynecomastia and skin laxity, such as plastic or cosmetic surgeons. Investigators will be selected based on interest and availability for participation in the study; ability to provide qualified subjects; adequate support staff; experience conducting clinical research; and willingness to comply with the protocol, IRB requirements, regulatory requirements (including the signed investigator agreement and statements disclosing any financial relationship investigators might have with Apyx Medical Corporation), and applicable regulations.

## 15.2 AMENDMENT POLICY

The investigator will not make any changes to this protocol without prior written consent from the Sponsor and subsequent approval by the IRB, except if the deviation from the protocol is necessary to protect the life and physical well-being of a subject in an emergency. Such protocol deviations must be reported to the Sponsor and the reviewing IRB as soon as possible, but no later than five working days after the emergency occurred.

Any permanent change to the protocol, whether it is an overall change or a change for specific study center(s), must be handled as a protocol amendment. Any amendment to the protocol that appears indicated as the study progresses will be fully discussed by the investigator(s) and the Sponsor. If agreement is reached regarding the need for an amendment, the Sponsor will write it. The written amendment must be submitted to the chairman of the IRB identified with this responsibility. Except for “administrative amendments”, investigators must await IRB approval of protocol amendments before implementing the change(s). Administrative amendments are defined to have no effect on the validity of the data or information resulting from the completion of the approved protocol, or the relationship of likely patient risk to benefit relied upon to approve the protocol; the scientific soundness of the investigational plan or protocol; and the right, safety or welfare of the human subjects involved in the investigation. When, in judgment of the chairman of the IRB, the investigators and/or the Sponsor, the amendment to the protocol substantially alters the study design and/or increases the potential risk to the subject, the currently approved written Informed Consent Form will require similar modification. In such cases, repeat informed consent will be obtained from subjects enrolled in the study before continued participation.

## 16. CONFLICT OF INTEREST POLICY

The independence of this study from any actual or perceived influence is critical. Therefore, any actual conflict of interest of persons who have a role in the design, conduct, analysis, publication, or any aspect of this trial will be disclosed and managed. Furthermore, persons who have a perceived conflict of interest will be required to have such conflicts managed in a way that is appropriate to their participation in the trial. The study leadership has established policies and procedures for all study group members to disclose all conflicts of interest and will establish a mechanism for the management of all reported dualities of interest.

## ATTACHMENTS: OUTCOME MEASURES

### ATTACHMENT A: PATIENT SATISFACTION QUESTIONNAIRE

*Please have the subject complete this assessment while referring to their image in the mirror and current post-treatment photos compared to baseline photos. Provide the subject with a mirror.*

*Using a mirror and reviewing your post-treatment photos, compare how your treatment area currently looks compared to your pre-treatment photos.*

1. On your **RIGHT** side, which, if any, changes do you see in the area treated?

- Less sagging skin
- Smoother skin texture
- Skin Feels Better
- Skin Feels Tighter
- Skin Appears Tighter
- Skin Looks more Radiant
- Skin Seems more Youthful
- Other: \_\_\_\_\_
- None

2. On your **LEFT** side, which, if any, changes do you see in the area treated?

- Less sagging skin
- Smoother skin texture
- Skin Feels Better
- Skin Feels Tighter
- Skin Appears Tighter
- Skin Looks more Radiant
- Skin Seems more Youthful
- Other: \_\_\_\_\_
- None

3. How would you characterize your satisfaction with the treatment on your **RIGHT** side?

- Very Satisfied
- Satisfied
- Slightly Satisfied
- Neither Satisfied or Dissatisfied
- Slightly Dissatisfied
- Dissatisfied
- Very Dissatisfied

4. How would you characterize your satisfaction with the treatment on your **LEFT** side?

- Very Satisfied
- Satisfied
- Slightly Satisfied
- Neither Satisfied or Dissatisfied
- Slightly Dissatisfied
- Dissatisfied
- Very Dissatisfied

5. Do you feel that one side of your chest looks better than the other (check one)?

YES       NO

a. If Yes, which side do you like better?

RIGHT       LEFT

6. Do you feel that the skin on one side of your chest feels tighter than the other (check one)?

YES       NO

a. If Yes, which side does the skin feel tighter?

RIGHT       LEFT

7. Do you feel the skin quality on one side of your chest is better than the other (check one)?

YES       NO

a. If Yes, which side has better skin quality?

RIGHT       LEFT

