## 2.2 POTENTIAL RISKS AND BENEFITS

### 2.2.1 POTENTIAL RISKS

This treatment modality was designed to inherently minimize the risk to the subject. However, treatment with energy-based modalities (laser, radiofrequency, and plasma devices) produce subsequent heating of the soft tissue that could involve the following commonly Expected Treatment Effects (ETEs): discomfort/pain, edema, erythema, ecchymosis, hypoesthesia, temporary sensory nerve injury (touch sensitivity, itching, temporary numbness/tingling), transient migratory firmness, and temporary and/or transient crepitus.

In addition to commonly expected treatment effects, treatment with the Renuvion APR device could involve the following risks: helium embolism into the surgical site due to inadvertent introduction into the venous or arterial blood supply system, unintended burns (deep or superficial), pneumothorax, pneumomediastinum, temporary or permanent motor nerve injury, ischemia, fibrosis, infection, gas buildup, bleeding, hematoma, seroma, subcutaneous induration, pigmentation changes, increased healing time, unsatisfactory scarring, asymmetry and/or unacceptable cosmetic result.

Risks associated with tumescent anesthesia (lidocaine and epinephrine) include blurred vision, mental/mood changes, drowsiness, dizziness, unusually slow heartbeat, rash, itching, swelling, anxiety, apprehensiveness, restlessness, tremor, weakness, sweating, palpitations, pallor, nausea and vomiting, headache, and respiratory difficulties.

Subjects using drugs that reduce coagulation (aspirin or NSAIDs) may experience increased bruising or bleeding at the treatment site. Any other medications prescribed for the procedure or after-procedure by the investigator have their own risks; these risks should be discussed with the subject.

A grounding pad is used to ground/neutralize the electrical current. Subjects undergoing radiofrequency treatment will be kept away from contact with metal parts which are grounded, or which have appreciable capacitance to earth.

As the Investigator will be treating the subjects per their Standard Practice of Care, there may be additional risks associated with the gynecomastia procedure. The Investigator will be responsible for properly reviewing all potential risks with the patient prior to treatment.

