##### **4.3.2 ADDITIONAL ENDPOINTS**

Other additional endpoints for this study are as follows:

1. Bilateral analysis of change to STPTUP (Tebbetts & Adams High 5 Measurements) from baseline to day 30, 90, and 180.
2. Bilateral analysis of change to STPTIMF (Tebbetts & Adams High 5 Measurements) from baseline to day 30, 90, and 180.
3. Bilateral analysis of male chest measurements (Murphy) from baseline to day 30, 90, and 180.
4. Bilateral analysis of skin excised during the procedure by Gynecomastia Grade (Rohrich Classification).
5. Bilateral analysis of gland tissue removal methods (Longheu) during the procedure by Gynecomastia Grade.
6. The Principal Investigator, sub-investigator or qualified clinician delegated by the principal investigator, will complete a bilateral PGAIS assessing overall aesthetic improvement in the treatment area at day 30, 90, and 180 post-treatment.
7. The subject will complete a bilateral SGAIS assessing overall aesthetic improvement in the treatment area at day 30, 90, and 180 post-treatment.
8. The subject will complete a bilateral Patient Satisfaction Questionnaire (PSQ) at the 180-day follow-up visit.

9. Baseline images compared to Day 30, 90, and 180 images will be assessed for correct identification of Renuvion-treated side by blinded IPRs.

[figure not shown]

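### The change checklist in the satisfaction questionnaire (items 1 and 2) pre-prints only favourable answers, so worsening of specific features is likely to be under-recorded in those two items

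*Protocol*

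**What the plan says.** Section 4.3.2, item 8, makes the questionnaire an additional endpoint: "The subject will complete a bilateral Patient Satisfaction Questionnaire (PSQ) at the 180-day follow-up visit". The form itself is printed in Attachment A.

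Items 1 and 2 put one question to each side of the chest: "which, if any, changes do you see in the area treated". The printed answers cover less sagging, smoother texture, better feel, tighter feel, tighter appearance, more radiance and, last, "Skin Seems more Youthful". A blank 'Other' line and 'None' follow.

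The same form then asks, for each side, "How would you characterize your satisfaction with the treatment on your" right or left side, on a scale that runs down to "Very Dissatisfied" (items 3 and 4). Items 5 to 7 ask for a comparison of the two sides, beginning with "Do you feel that one side of your chest looks better than the other".

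Outside the questionnaire, section 4.3.2, item 7, states: "The subject will complete a bilateral SGAIS assessing overall aesthetic improvement in the treatment area at day 30, 90, and 180 post-treatment". Section 4.3.1 makes adverse events on both sides the primary safety endpoint, and section 2.2.1 lists cosmetic harms among the device risks: "pigmentation changes, increased healing time, unsatisfactory scarring, asymmetry and/or unacceptable cosmetic result".

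**The concern.** The question in items 1 and 2 is neutral, since it asks what changed. The answers are not neutral, because every printed change is a gain. A subject who notices tighter skin is prompted and ticks a box. A subject who notices looser or rougher skin gets no prompt and must think to write it in. Free text is generally used less than tick boxes, so the two directions of change are not collected on equal terms.

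This matters because the subject is blinded to the treated side (section 7.2), and these are the only subject-completed items that itemise absolute change, feature by feature, for each side. The analysis is descriptive (section 10.1), so counts of ticks by side are a natural output. With at most 10 treated subjects (section 10.2), a few unprompted worsenings would alter how such a table reads. The form is also fixed in the protocol, and analysis cannot recover answers that it never prompted.

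**Working it through.** No figure in the protocol is at issue, so the check is a count of response options followed by a comparison of the instruments.

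**Step 1. Options per side.**

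| Instrument | Favourable | Neutral or none | Unfavourable | Free text |
|---|---|---|---|---|
| Questionnaire items 1 and 2 (Attachment A) | 7 | 1 ('None') | 0 | 1 ('Other') |
| Questionnaire items 3 and 4 (Attachment A) | 3 | 1 | 3 | 0 |
| Subject aesthetic improvement rating (Table 5) | 3 | 1 | 3 | 0 |

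The two overall ratings are balanced and the checklist is not. (Section 4.3.3.5 also describes the aesthetic scale as having 5 points, whereas its tables show 7. Both versions include a worse grade, so the comparison is unaffected.)

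**Step 2. What a tick-count can show.** Take one feature on one side in n subjects. Let b be the number who see it better, u unchanged and w worse, so n = b + u + w. If every subject who sees an improvement ticks it, the count is b. The remainder, n − b = u + w, is not split by the printed options. Any split depends on 'Other'. If a share f of the w subjects writes the worsening in, recorded worsening is f × w, which runs from 0 (f = 0) to w (f = 1). The protocol gives no information on f, so the size of the under-recording cannot be computed. Only its direction is known: with b the same on both sides, a difference in w does not show in the ticks.

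**Step 3. Whether another instrument fills the gap feature by feature.**

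- Items 3 and 4 allow dissatisfaction with each side, but overall and without naming a feature.
- The subject's aesthetic rating allows three grades of worsening per side at Days 30, 90 and 180, but again overall.
- Items 5 to 7 cover looks, tightness and skin quality, but only as a preference between sides. One side improved and the other unchanged gives the same answer as one side unchanged and the other worse.
- The photographic reviewers choose which side was treated (section 4.3.3.7). They do not grade features.
- All expected treatment effects and adverse events are collected (section 8.1.1), and subjects are interviewed at each follow-up visit (section 8.3). The synopsis adds a visual examination of the treated area. This covers colour, scarring and numbness. Looser or rougher skin is less certain to be reported, because section 8.1.1 defines an adverse event as a new or exacerbated medical problem.

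**Result.** Overall worsening by side is captured more than once. Worsening of a named cosmetic feature, as the subject sees it, is prompted nowhere.

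**The case against.** A reader might infer that a side seen as worse ends up recorded as 'None', and that harm therefore disappears from the comparison of sides. The documents do not support either step. 'Other' is offered for each side directly before 'None', and a subject who sees a deterioration and follows the question would use it. Harm is also visible elsewhere: the same blinded subject grades each side three times on a scale with three worse categories, rates dissatisfaction by side in items 3 and 4, and is interviewed for adverse events at every follow-up visit. The device risks quoted from section 2.2.1 belong to that safety collection, so repeating colour, scar and numbness on a satisfaction form would duplicate it. An example with invented counts of lost worsenings would prove nothing, because it would have to assume that 'Other' stays blank and that the other instruments do not exist.

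It is also fair to say that the questionnaire is the eighth of nine additional endpoints, completed once, in a descriptive pilot, and that no success criterion rests on items 1 and 2.

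All of this stands, and it limits the point to these two items and to low severity. It does not remove the imbalance, because the overall ratings do not say which feature worsened and the checklist that could say so prompts in one direction only.

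**Conclusion.** The point holds in limited form. Items 1 and 2 offer 7 favourable printed answers and 0 unfavourable ones per side. Feature-level worsening is therefore likely to be under-recorded there, and tick-counts by side show only benefit or its absence. The conclusion rests on one assumption from outside the protocol, that free text is used less readily than a tick box. The amount of under-recording cannot be estimated from the document.

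This is a low-severity response bias confined to two items of one additional endpoint. It is not a failure to detect harm, and it does not touch the primary safety endpoint.

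**What to change.** Before the form is first used, give each feature listed in items 1 and 2 a better / same / worse answer for each side, or add an unfavourable option to match each favourable one. State that better and worse will be tabulated separately by side and that 'Other' entries will be coded by direction, preferably by someone unaware of which side was treated. State also that items 1 and 2 will not be presented alone as evidence of benefit, but alongside items 3 and 4 and the subject's bilateral aesthetic rating. Extra lines for colour, scar and numbness are not needed.

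The cost is a revision to a short form and notice to the IRB. The downside is loss of direct comparability with any earlier use of the questionnaire. If the form is already in use, coding 'Other' by direction and restricting the interpretation can still be done, but neither recovers answers that were never prompted.

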***Thank you for completing this questionnaire.***

Subject Initials: \_\_\_\_\_

Date: \_\_\_\_\_ (DD/MON/ YYYY)

## APPENDIX PROTOCOL REVISIONS LOG

VERSION	DATE	SIGNIFICANT REVISIONS
